The HCRV program was started to combat these issues. A designated outreach specialist works with incarcerated VHA-eligible Veterans to establish a post-release plan for linkage to VHA services (2014). This program, with 1-2 outreach specialists per state, has improved the connection between reentry Veterans and the VHA. However, our analyses of homeless program data linked to CDW indicate that 43% of eligible HCRV Veterans **do not** have a VHA outpatient contact in the first 4 months post incarceration. Reducing this number is critical given the elevated rates of chronic health conditions, as well as MH or SUDs in this population (Noonan 2007; Taxman 2010; Maruschak 2012). To address this gap, we will work with the national HCRV office to implement an evidence-based peer support intervention to extend the reach and effectiveness of the HCRV program in linking Veterans to VHA. Peers with incarceration experience are likely to better understand and connect with Veterans on a personal level than the outreach specialist, and thus are more likely to maintain contact and link to VHA during the first months post-release (Blodgett 2013; Chinman, George et al. 2014; Bagnall, South et al. 2015). Peers are gaining popularity in forensic settings (called “forensic peer specialists”) with civilian populations and would likely be beneficial for a Veteran population (Miller and Massaro 2008). The aims of this project are,

1. Conduct contextual analysis to identify VA and community reentry resources, and to describe how reentry Veterans use them.
2. Implement peer-support to link reentry veterans to VHA primary, mental health, and SUD services. We will use external and internal facilitation as the implementation strategy.
3. At the end of this project, we will develop a proposal for a multi-VISN expansion study, which will use a hybrid type III, stepped-wedge design, to demonstrate effectiveness in multiple geographic and contextual settings.

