of the first Veteran-peer encounters will involve accompanying the Veteran to his first VHA health care appointment and orienting him to check-in, appointment making, laboratory, and pharmacy. Other encounters may include reviewing health-related priorities and goal setting, assistance with health tasks (e.g. refilling prescriptions), and brief motivational interviewing related to health goals. Training of peers will be conducted by Drs. [name], [name], [name] and [name], over a 4-day period, at Bedford VAMC. Following training, the HCRV team (VISN coordinator(s), outreach specialists, and peers) will participate on twice monthly conference calls, led by the trainers and the external facilitators ([name] and [name]), to discuss issues that arise in the use of peer support.

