Project Plan Overview: We propose to implement the Post Incarceration Engagement intervention in Massachusetts using a facilitation implementation strategy. We conduct formative and summative analyses, including assessment of fidelity, and a matched comparison group to evaluate the intervention's Veteran outcomes of linkage and engagement in VHA health care (using health care utilization measures). The project proceeds in 3 phases (see Figure 1). First, in preparation for implementation of peer-support intervention in the first state, we will conduct a contextual analysis in MA of the resources available in VHA and in community organizations to meet the needs of Veterans released from incarceration (Aim 1), development of peer-support guidebook (based on findings of the contextual analysis) and hiring of 2 peers. Next the intervention will be implemented in MA (Aim 2). It will last 6 months with a total of 30 Veterans receiving the peer support. We will identify a matched sample of comparison reentry Veterans. Qualitative formative and summative interviews will be conducted with a sample of stakeholders and Veterans to assess fidelity of the intervention. A review of peer worksheets documenting contacts with Veterans will also help evaluate fidelity evaluation. Utilization of VHA primary care, mental health care, and SUD care will be evaluated through chart reviews, and self-report (self-report for intervention Veterans only). Finally we will develop a proposal for the spread of this intervention through the use of a cluster-randomized multi-VISN hybrid implementation-effectiveness study (Aim 3).

Design and Methods: Key Outcomes: Our Veteran level outcomes include # of primary care visits, MH visits, and SUD visits (where diagnosis indicates appropriateness); and missed opportunity rates (no-shows and cancellations) for primary care, MH, and SUD visits. Secondary outcomes include # of emergency room (ER) visits, hospitalizations, and hospital days – these are also being assessed in the BridgeQUERI MISSION project, providing cross-project comparisons. Our main implementation outcome will be fidelity of the intervention as implemented, in comparison to core elements as contained in the peer-support guidebook. We use a practical approach based on the NIH's Behavioral Change Consortium fidelity framework for psychosocial Treatments (Bellg, Borrelli et al. 2004). Our two primary fidelity measures are number of peer

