Phase 1: Contextual Analysis and Preparation for Implementation in Massachusetts. We will conduct contextual analysis (Chambers, Mustard et al. 2013; Chambers, Glasgow et al. 2013; Lyon, Pullmann et al. 2015) through interviews and network mapping (Aim 1). At the end of this phase the findings will be incorporated into the peer-support guidebook. This phase will involve interviewing Veterans (thrice over 6 months) and stakeholders (once). Network mapping is a technique used in business and engineering, and is increasingly being applied in health care. It involves documenting potential paths that individuals and groups follow in the process of accomplishing a task (here, linkage to primary care and other health services)(Lyalin and Williams 2005; Williams, Lyalin et al. 2005; Rico, Yalcin et al. 2014). We use interview questions that seek temporal, spatial, and participatory information. The timing, sequence, and duration of Veterans' contacts with individuals and organizations are mapped in an activity diagram (Lyalin and Williams 2005), which are then combined to comprehensively map the network of reentry-related contacts that Veterans make. These maps may reveal unhelpful contacts, waiting between contacts, and useful but infrequently tapped resources. Population: There are about 200 Veterans, released from Massachusetts prisons each year. Recruitment of Veterans: We will use a method currently in use VHA by a contractor, Policy Research Associates (Delmar, NY), to contact reentry Veterans. During prison visits, the outreach specialists will collect contact information from incarcerated Veterans who indicate willingness to participate in the project after their release. The outreach specialist will provide our team with the contact sheets of those Veterans and their release dates. We will contact these Veterans after their release, enrolling 10 Veterans. Inclusion/Exclusion: Released from an MA state prison, eligible for VHA services, and no history of dementia.

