Additional Design Considerations: The focus of the *Post-Incarceration* project is to develop implementation methods, materials and training, identify appropriate level of internal facilitation, and assess dissemination processes across different states. It is not designed to demonstrate a statistically significant effect of the intervention. With the anticipated sample size of 30 in the peer-support intervention groups and the 30 in the comparison group, the linkage rate, now at 57%, would need to increase by at least 20% to detect the intervention effect with 80% power at the 0.05 significance level. However, our measurement of these outcomes in the current project will allow us to estimate effect sizes and sample sizes for the next phase of this implementation, i.e. a cluster-randomized multi-VISN hybrid implementation-effectiveness study (this next phase will occur after the current project, supported by a separate funding source).

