Analysis Plan

Official Title: Veterans Justice Reentry (Post-Incarceration) (QUE 15-284)

Brief Title: Improving Linkage to Health and Other Services for Veterans Leaving Incarceration (PIE)

ClinicalTrials.gov ID: NCT02964897

Unique Protocol ID: QUX 16-012

Study Principal Investigator: D. [name] MS BA

Document date: September 7, 2021

Analysis Plan:

Improving Linkage to Health and Other Services for Veterans Leaving Incarceration (ID QUX 16-012)

We will enroll Veterans on a rolling basis as released from MA correctional facilities. We will use HOMES database to create a historical comparison group comprised of all Veterans released in MA in the two-year period directly preceding the start of the PIE intervention and who accessed VA Health Care for Reentry Veterans (HCRV) services.

Quantitatively, we will use HOMES and CDW to compare intervention and comparison Veterans with respect to their baseline demographic characteristics (age, gender, race, ethnicity, marital status, self-rated health) and our outcomes interest. Also for intervention Veterans we will have self-report diagnoses and utilization from baseline and 6-month follow up (including utilization of non-VA health care sources). We will compare rates of visits for primary care, outpatient MH treatment, outpatient SUD treatment, as well as missed opportunities (e.g. no shows) between intervention and comparison groups using t-tests and chi-square tests. For our secondary measures we will also compare intervention to comparison on ER and hospital use (episodes and # of days) during the 6-month reentry period.

Analysis involves two phases. First, we use descriptive statistics to summarize the volume and intensity of peer activities in support of the Post-Incarceration Engagement (PIE) intervention participants. Secondly, to examine access to and engagement in care outcomes, we compare our measures of linkages to VA health care following release between PIE participants and our historical comparison group. Specifically, we use bivariate tests (Chi-Square/Fisher Exact Tests and t-tests, as appropriate) to assess the relationship between participation in the PIE intervention and linkages with VA health care.

Summary of key variables

- Demographics (age, gender, race, ethnicity, marital status, self-rated health)
- SUD diagnoses
- MH diagnoses
- Criminal offense
- Length of incarceration
- # of arrests
- Housing/homeless experience
- Major comorbidities (out of list of 10-12)

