- Visits to primary care
- Visits to MH outpatient care
- Visits to SUD outpatient care
- ED encounters
- Inpatient hospitalizations
- No shows at the above appointments

All data will be stored on VINCI and all analysis will be conducted on VINCI

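### Does the SAP's shorthand for missed appointments leave the protocol's missed-opportunity rate undefined?

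*SAP*

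**What the plan says.** Protocol, section 3 (Procedures), Key Outcomes, includes among the Veteran-level outcomes "missed opportunity rates (no-shows and cancellations) for primary care, MH, and SUD visits". Emergency room and hospital use follow in a separate sentence as secondary outcomes.

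The SAP's analysis paragraph compares visit rates for primary care, MH and SUD treatment, "as well as missed opportunities (e.g. no shows) between intervention and comparison groups using t-tests and chi-square tests". Emergency and hospital use again have their own sentence, as secondary measures. Under Summary of key variables the SAP lists visits to the three outpatient services, then ED encounters and "Inpatient hospitalizations", and last "No shows at the above appointments".

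The SAP mentions neither cancellations nor scheduled appointments. Neither document states a denominator, a unit of analysis, or the handling of a Veteran who has no appointment.

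**The concern.** Three things look wrong. The protocol counts cancellations and the SAP does not name them. The protocol wants a rate, but the SAP list holds only attended visits and no-shows. And the no-show line refers back to a list that includes ED and inpatient entries, which the protocol keeps out of this outcome.

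The choice of measure could matter because the intervention may change how many appointments are made. Peers' early contacts include "accompanying the Veteran to his first VHA health care appointment and orienting him to check-in, appointment making, laboratory, and pharmacy". If peer support raises bookings, a simple count of no-shows can rise even when each appointment is as likely to be kept as before. If peers persuade Veterans to cancel rather than not turn up, a no-show-only rate improves while the protocol's rate is unchanged. The protocol's Additional Design Considerations say that "our measurement of these outcomes in the current project will allow us to estimate effect sizes and sample sizes for the next phase", so a badly defined measure could be carried into the planning of the later study.

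**Working it through.** The plan states no missed-opportunity rate, no-show rate, cancellation rate or number of bookings, so there is no figure to reproduce. The check compares the texts and then illustrates with assumed inputs.

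**1. What the texts settle**

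| Element | Protocol, Key Outcomes | SAP |
|---|---|---|
| Form | Rate | *Rates* opens the sentence and may extend to missed opportunities |
| Numerator | No-shows and cancellations | No-shows, given as an example |
| Services | Primary care, MH, SUD | Same three in the analysis sentence; the list is loosely worded |
| Denominator, unit | Not stated | Not stated |

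Nothing in the SAP's analysis text contradicts the protocol. The list does not claim to be complete. It omits hospital days, peer activity and self-reported non-VA use, all of which the SAP text commits to. Absence from the list is therefore weak evidence that cancellations will not be extracted.

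**2. Is a scheduled-appointments field needed?** Not strictly. Scheduled = attended + no-shows + cancellations, provided walk-in visits are kept apart. Cancellations are the one indispensable addition, and the protocol names them.

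**3. Cost of leaving cancellations out** (all inputs assumed, per 100 scheduled appointments)

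Protocol rate = (no-shows + cancellations)/100. No-show-only rate = no-shows/(visits + no-shows). Start with 20 no-shows, then let 5 of them become cancellations.

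| Cancelled at start | No-show-only rate | Change (points) | Protocol rate |
|---|---|---|---|
| 10 | 20/90 = 22.2% to 15/85 = 17.6% | -4.6 | 30%, unchanged |
| 15 | 20/85 = 23.5% to 15/80 = 18.8% | -4.8 | 35%, unchanged |
| 30 | 20/70 = 28.6% to 15/65 = 23.1% | -5.5 | 50%, unchanged |

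The order of two groups can even reverse. Ten no-shows with 30 cancellations give a protocol rate of 40% and a no-show-only rate of 10/70 = 14.3%. Twenty no-shows with 10 cancellations give 30% and 20/90 = 22.2%.

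**4. Cost of using a count.** Mean no-shows = mean bookings x no-show rate per appointment. The protocol's current linkage is 57%. Reading its 20% increase as 20 points gives 77%. If unlinked Veterans never book, and the no-show rate and bookings per linked Veteran are the same in both groups, the count ratio is 0.77/0.57 = 1.35. Reading 20% as relative gives 0.684/0.57 = 1.20.

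If instead the newly linked would each have booked once and missed, take 6 bookings per linked Veteran and 20% no-shows. The comparison count is 0.57 x 6 x 0.2 + 0.20 = 0.884. The intervention count, with that first visit now kept, is 0.57 x 6 x 0.2 + 0.20 x 5 x 0.2 = 0.884, a ratio of 1.00. So the size depends on the assumption. More to the point, the protocol asks for a rate, so this is not the outcome it calls for.

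**5. Precision.** Suppose 23 of 30 intervention Veterans have an appointment (0.77 x 30 = 23.1), with 35% missed, 6 bookings each and intra-Veteran correlation 0.1. The variance of a Veteran's rate is 0.35 x 0.65 x (0.1 + 0.9/6) = 0.0569, so the SD is 0.238. Apply 57% to the comparison group:

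- 30 Veterans, so 17 with an appointment: half-width of the 95% interval = 2.02 x 0.238 x sqrt(1/23 + 1/17) = 15.4 points.
- 400 Veterans (the SAP's two-year historical group, capped by the protocol's "There are about 200 Veterans, released from Massachusetts prisons each year"), so 228 with an appointment: 1.97 x 0.238 x sqrt(1/23 + 1/228) = 10.3 points.

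When bookings vary between Veterans (geometric, mean 4 to 8; correlation 0.05 to 0.20), simulation puts the half-width at about 12 to 24 points.

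**The case for a change.** The strongest reply is that a SAP exists to remove such choices before the data are seen. A count, an any-no-show indicator and a proportion would all fit t-tests or chi-square tests. Nothing says whether the outcome was deliberately narrowed to no-shows. Wide intervals do not excuse a loose definition, because a planning estimate should at least estimate the intended quantity. Adding a sentence would be cheap.

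Part of this stands. The SAP is terser than the protocol, and its last list item is badly placed. But for numerator, form and services the remedy only repeats what the protocol says. Whatever goes beyond that is debatable:

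- Restricting to Veterans with an appointment conditions on something the intervention can change. If newly linked Veterans have a 30% no-show risk and the others 20% (assumed), the intervention rate is (0.57 x 0.2 + 0.20 x 0.3)/0.77 = 22.6% against 20%, although no individual got worse.
- A per-Veteran mean gives one booking the weight of six. In the book-once-and-miss case, the comparison group's per-Veteran mean is (0.57 x 0.2 + 0.20)/0.77 = 40.8%. Over appointments it is 0.884/(0.57 x 6 + 0.20) = 24.4%.
- Whether clinic-initiated or rescheduled cancellations count is a matter of judgement.

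The link to the next study is also looser than it looks. The sentence on effect sizes follows one about the linkage rate alone. Its 57% is the complement of the 43% who the Specific Aims say do not "have a VHA outpatient contact in the first 4 months post incarceration"; it is not a booking rate.

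The ED and inpatient reading is the weakest part. ED encounters and admissions are not ordinarily appointments, and both documents treat them apart from missed opportunities.

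**Conclusion.** The difference in wording is real, but it is missing detail that a competent analyst fills from the protocol. The documents do not show that the planned data cannot yield the protocol's rate. They show only that the SAP does not spell it out.

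If cancellations were in fact left out, the illustrated effect is a shift of 4.6 to 5.5 points, and group order could reverse under some mixes. These figures rest wholly on assumed no-show and cancellation frequencies. That shift is small beside a half-width of 10 points or more for this comparison, which is itself based on assumed bookings and correlation. No design figure or linkage analysis depends on it.

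The remaining choices have no clearly better answer to write in. It is enough that the report states the definition used and gives the proportion of Veterans with any appointment beside the rate. No amendment is needed.

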Phase 2 - MA Implementation of Peer Support. This phase involves implementation and evaluation of the peer-support intervention in MA. For Population, Recruitment of Veterans, Inclusion/Exclusion, see Phase 1, above. Our target is 30 Veterans receiving peer support. We will enroll Veterans on a rolling basis as released from MA correctional facilities. We will use HOMES database to create a matched comparison group of Veterans released in the same time period in MA, matching on demographics, SUD/MH diagnoses, criminal offense, length of incarceration, and # of arrests. Intervention will last for 6 months for any single Veteran, with peers having caseloads of 15 Veterans (Dihoff 2009). A VISN 1 outreach specialist, [name], will serve as

internal facilitator, while [name] and [name] will be external facilitators. Peer Training: see above in “Peer-Support Intervention”.

Data Sources, Collection and Analysis: Peers will administer a health care utilization questionnaire with intervention Veterans at baseline (week 1) and at 6 months to capture information about VA and non-VA health service use (the former for comparison with VA medical record data).

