Analysis: During implementation we will collect formative evaluation data about the intervention through interviews (5 stakeholders and 5 Veterans). We will assess elements of the implementation by learning what meanings the participants (stakeholder, peers, Veterans) assign to the intervention and the processes that the intervention is designed to affect (Orlikowski and Baroudi 1991). We will also conduct summative evaluation, including qualitative interviews (5 Veterans and 5 stakeholders) to evaluate, for example, whether peers were *Enabling* linkage to and engagement in health care, and whether this helped address Veteran’s health care *Need*. With stakeholders we will explore the effectiveness of external and internal facilitation, and identify facilitators and barriers to implementation. Quantitatively, we will use HOMES and CDW to compare intervention and comparison Veterans. Also for intervention Veterans we will have self-report diagnoses and utilization from baseline and 6-month follow up (including utilization of non-VA health care sources). We will compare rates of visits for primary care, MH, and SUD between intervention and comparison groups using t-tests and chi-square tests. For our secondary measures we will compare intervention to comparison Veterans on ER and hospital use (episodes and # of days) during the 6 month reentry period.

Key Covariates. We will use CDW and HOMES data to evaluate whether there are substantial differences between the intervention and comparison Veterans at baseline. This approach accounts for the possibility that observed differences in our outcomes, such as linkage rates, may be partially explained by factors such as duration of sentence, severity of crime, number of incarcerations, ever used VHA services, length of time since last used VHA services, and socio-demographics such as age and race.

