4. IMPACT

The implementation work described here is highly aligned with our operational partners in the national HCRV program (see letter of support) who recognize many HCRV Veterans are not linking to VHA, and likely are receiving inadequate care from a patchwork of sources. It helps address the known challenge for HCRV of overcoming reentry Veterans’ mistrust of and past negative experiences with large systems – a process that data indicate is best done by a peer. Our project will help answer the question of whether peer-support for Veterans after their incarceration increases VHA linkage rates. Also the project will provide a roadmap (with guidebook, training materials and implementation strategies) so that other states and VISNs can efficiently adapt and implement this peer-support approach in their HCRV programs. The ultimate impact will be an increased rate of linkage to VHA services, substantially beyond the current 57% rate. This linkage will help contribute to improved health and mental health of the thousands of Veterans released from incarceration annually. It has the potential to prevent the cascade of events for many former offenders, when health and mental health deterioration rapidly lead to negative behaviors, re-offending and more incarceration.

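### Does comparing ER and hospital use from HOMES and CDW, with non-VA use known only for PIE Veterans, require a change to the plan?

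*SAP*

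**What the plan says.** The SAP's analysis plan states the secondary comparison in one sentence: "For our secondary measures we will also compare intervention to comparison on ER and hospital use (episodes and # of days", for the six months after release. That sentence names no source. The source comes earlier in the same paragraph: "we will use HOMES and CDW to compare intervention and comparison Veterans", on baseline characteristics and outcomes. The Protocol (section 3, Phase 2, Analysis) says the same: "Quantitatively, we will use HOMES and CDW to compare intervention and comparison Veterans".

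Non-VA care enters by another route. For intervention Veterans the SAP adds self-reported "utilization from baseline and 6-month follow up (including utilization of non-VA health care sources". The Protocol's Phase 2 data-collection paragraph has peers give a questionnaire at week 1 and at 6 months "to capture information about VA and non-VA health service use", with the VA part to be checked against the VA record. The Project Plan Overview says that use of primary, mental health and SUD care will be "evaluated through chart reviews, and self-report (self-report for intervention Veterans only". No non-VA source is named for the comparison group.

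ER visits, hospitalizations and hospital days carry no VA qualifier in either document, whereas primary, mental health and SUD care is tied to the VHA in the Project Plan Overview.

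**The concern.** The intervention could change how much acute care the records see. Aim 2 is to "Implement peer-support to link reentry veterans to VHA primary, mental health, and SUD services", and the Protocol's Impact section says that "many HCRV Veterans are not linking to VHA, and likely are receiving inadequate care from a patchwork of sources". If a linked Veteran goes to a VA emergency room where an unlinked one would have gone to a community hospital, VA-recorded use rises with no change in total use. A real fall in total acute use could then look smaller, vanish or appear as a rise, and part of a change of site could be read as an effect of PIE.

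Two features add to the worry. The Specific Aims link poor linkage to inefficient emergency and hospital use without limiting this to VA sites, so a reader may test that idea against this comparison. The Key Outcomes paragraph also expects to set these outcomes beside those of the MISSION project.

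**Working it through.** The plan gives no rate, effect size or power for ER or hospital use, so there is no figure to reproduce. The check is whether the comparison is sound as specified, and what can be said about its distance from total use.

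**1. Sources by group**

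| | PIE | Comparison |
|---|---|---|
| HOMES and CDW | yes | yes |
| Self-report, VA and non-VA | yes | no |

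The between-group contrast rests on the first row, which is the same for both groups. The second row is presented as an addition for intervention Veterans. The documents do not say whether CDW holds any non-VA care; that it does not is an inference from the separate questionnaire.

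**2. Relation to total use**

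Recorded ratio = true ratio of total use × (VA share in PIE ÷ VA share in comparison).

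If the shares are equal, the recorded ratio is unbiased, although absolute differences shrink. The documents give neither share.

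**3. Illustration on assumed shares**

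Assume VA shares of acute care of 0.60 in linked Veterans (sL) and 0.20 or 0.40 in unlinked Veterans (sU), with equal total use in both. The group share at linkage p is p × sL + (1 − p) × sU. Take p = 0.57 in the comparison group and, in PIE, either 0.57 × 1.2 = 0.684 or 0.57 + 0.20 = 0.77. These are proxies: 57% reflects any VHA outpatient contact within four months, and the 20% under Additional Design Considerations is a detectable difference, not an expected effect.

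| p in PIE | sU | Share in PIE ÷ share in comparison | True 10% fall appears as | True 20% fall appears as |
|---|---|---|---|---|
| 0.684 | 0.40 | 0.5368 ÷ 0.514 = 1.044 | 0.940 | 0.835 |
| 0.684 | 0.20 | 0.4736 ÷ 0.428 = 1.107 | 0.996 | 0.885 |
| 0.77 | 0.40 | 0.554 ÷ 0.514 = 1.078 | 0.970 | 0.862 |
| 0.77 | 0.20 | 0.508 ÷ 0.428 = 1.187 | 1.068 | 0.950 |

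Inflation is 4% to 19%. A 10% fall is reversed in one case of four, a 20% fall in none.

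**4. Sensitivity to the assumptions**

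Setting the group shares directly at 57% (comparison) and 77% (PIE) gives 0.77 ÷ 0.57 = 1.35, so a true ratio of 0.80 appears as 1.08. At 40% and 77% the factor is 0.77 ÷ 0.40 = 1.93. If PIE instead had the lower share (57% against 77%), then per 100 comparison events a true change of −20 would appear as 80 × 0.57 − 100 × 0.77 = −31.4, an overstated fall. The size, and even the sign, therefore follow from the assumed inputs.

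**5. If linkage itself lowers use**

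Let total use be k times as high when unlinked as when linked. Recorded use falls as linkage rises only if k × sU > sL, that is, k > 0.60 ÷ 0.40 = 1.5 or k > 0.60 ÷ 0.20 = 3. The documents give no k.

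**6. Sampling variation**

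At an assumed one visit per Veteran, 30 PIE Veterans give a 95% factor of exp(1.96 ÷ √30) = 1.43 either way. This ignores variation in the comparison group and any overdispersion, both of which would widen it. It exceeds every inflation in the table of step 3.

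**7. What a change would alter**

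A VA-recorded label changes neither the data, the test nor the estimate. A table of PIE Veterans' non-VA use would only tabulate data already planned. A sensitivity range of assumed capture ratios would return its own assumptions.

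**The case for a change.** The strongest case for a change is that the possible bias arises from the intervention itself, which a larger follow-on study would not average away. The Protocol says its measurements will help size that study and be compared across projects, and a label costs almost nothing. Accessing HCRV does not ensure VA capture: the Specific Aims report that 43% of eligible HCRV Veterans had no VHA outpatient contact in the first four months. Adding PIE self-reported non-VA use to one side only would also do harm: with 57% capture in the comparison group, a true ratio of 0.80 would appear as 0.80 ÷ 0.57 = 1.40.

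Much of this stands. The records cannot be assumed to cover total acute use, and a report should not claim that they do. But the Project Plan Overview already describes the Veteran outcomes as linkage and engagement in VHA care, and the named sources and the separate non-VA questionnaire point the same way. The SAP does not propose to add self-report to the contrast. The Impact section's stated goal is the linkage rate, not fewer ER visits. Whether the comparison with MISSION is like with like depends on how MISSION measures these outcomes, which the documents do not say. If the follow-on study wants total acute use, it will need a source for it in every group; no wording in this SAP supplies one.

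The direction is also less certain than it seems. The planned guidebook covers community services as well as VHA services, so peers might raise non-VA use too.

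**Conclusion.** No change to the plan is needed. Followed as written, it gives a coherent comparison of VA-recorded ER and hospital use from the same sources in both groups. The missing qualifier is a gap that an analyst would fill from the named data sources, and filling it changes no result.

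The underlying fact is correct: unless CDW holds non-VA care equally for both groups, the comparison could understate or overstate a change in total acute use. Its size is unknown. The 4% to 19% inflation rests on assumed VA shares, equal total use in linked and unlinked Veterans, and proxy linkage figures. It is smaller than the sampling factor of about 1.43, in secondary outcomes of a project that the Protocol says was not designed to establish a significant effect. Calling the outcomes VA-recorded in the report, and keeping PIE self-report descriptive and outside the contrast, would be ordinary good practice in writing up.
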